### Secondary Efficacy Endpoint

• Time from Randomization (Week 12) to Relapse in all subjects irrespective of age for ecopipam compared to those receiving placebo during the double-blind, R/WD period.

Exploratory Efficacy Endpoints which may be considered Secondary Efficacy Endpoints if there is a 100% Correlation with the Primary Efficacy Endpoint

- Time from Randomization (Week 12) to a worsening by at least one category of the Global Impression Tourette's Syndrome of Severity (CGI-TS-S) in subjects ≥ 6 and < 18 years for ecopipam compared to those receiving placebo during the double-blind, R/WD period.
- Time from Randomization (Week 12) to a worsening by at least one category of the CGI-TS-S in all subjects for ecopipam compared to those receiving placebo irrespective of age.

10.2.1. Time from Randomization (Week 12) to Relapse in all subjects irrespective of age for ecopipam compared to placebo during the double-blind R/WD period (Secondary Efficacy Endpoint)

#### Statistical analysis:

A secondary analysis will be performed irrespective of age. The analysis method will be the same as the primary efficacy analysis as described in Section 10.1.

10.2.2. Time from Randomization (Week 12) to a worsening by at least one category of the CGI-TS-S in subjects ≥ 6 and < 18 years for ecopipam compared to placebo during the double-blind, R/WD period

The Clinical Global Impression of Tourette Syndrome (CGI-TS) consists of two reliable and valid 7-item Likert scales used to assess severity and change in clinical symptoms. The severity scale (CGI-TS-S) ranges from 1 (Normal, not ill) to 7 (extremely ill). The improvement scale (CGI-TS-I) ranges from 1 (very much improved) to 7 (very much worse) with a score of 1 or 2 defining positive response.

The severity rating is based upon observed and reported symptoms, behavior, and function in the past seven days with the score reflecting the average severity level across the seven days. The efforts of peers, teachers and parents to assist, accommodate, or support the subject should be considered in overall severity.

Severity will be assessed at Screening, Baseline and at Weeks 4, 8, 12, 13, 14, 15, 16, 18, 20, 22 and 24. Improvement will be assessed at Baseline and at Weeks 4, 12, 13, 14, 15, 16, 18, 20, 22 and 24.

Sponsor: Emalex Biosciences, Inc.; Protocol No.: EBS-101-TD-301

The Severity scale ranges from: 1=normal, not at all ill; 2=borderline mentally ill; 3=mildly ill; 4=moderately ill; 5=markedly ill; 6=severely ill; 7=among the most extremely ill patients where the improvement scale ranges from: 1=very much improved; 2=much improved; 3=minimally improved; 4=no change; 5=minimally worse; 6= much worse; 7=very much worse."

### Statistical analysis:

This is a time-to-event endpoint not related to Relapse which will rely on a treatment policy strategy. A cumulative incidence approach will be used to account for the competing risk of study discontinuation due to Relapse. Gray's test will be used to test for a statistically significant treatment difference (Gray 1988). Cause-specific Cox proportional hazards regression model will be used to obtain the hazard ratio and its 95% CI for time to worsening (Cox 1972). In this model, subjects who complete or discontinue from the double-blind randomized withdrawal period before meeting endpoint criteria (worsening by at least one category of the CGI-TS-S) and for reasons not related to Relapse (such as Adverse Event, Pregnancy etc. as captured in eCRF) will be censored at the time of discontinuation.

The correlation in subjects ≥ 6 and < 18 years, between meeting relapse criteria based on YGTSS-TTS and having at least a 1-point reduction on CGI-TS-S will be assessed at the visit where relapse occurs. If there is a 100% correlation of this endpoint i.e. 100% of subjects who would have met Relapse criteria based on the YGTSS and at least 90% completed CGI-TS-S for subjects with completed YGTSS-TTS, also had at least a 1-point decrease on the CGI-TS-S (i.e. these two types of events occur simultaneously) then it may be considered as a secondary endpoint with agreement from Health Authorities. The strong correlation would suggest Relapse is not a competing risk.

10.2.3. Time from Randomization (Week 12) to a worsening by at least one category of the CGI-TS-S in all subjects for ecopipam compared to placebo irrespective of age.

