- Time from Randomization (Week 12) to treatment discontinuation during the double-blind R/WD period for ecopipam compared to placebo.
- Time from Randomization (Week 12) to loss of ≥ 100% of the improvement experienced on the Yale Global Tic Severity Scale- Total Tic Score (YGTSS-TTS) from Baseline (Day 1) to the last visit (Week 12) in the open-label Stabilization period for ecopipam compared to placebo.
- To evaluate the population PK/pharmacodynamic (PD) relationships with ecopipam during the open-label Stabilization period of the study.

Protocol EBS-101-TD-301 Version 9.0, 05 March 2024

Additional analyses will include efficacy endpoints listed above at all earlier timepoints, and the YGTSS subscales individually (Motor, Vocal, and Impairment). The correlation between subjects meeting Relapse criteria based on YGTSS-TTS and those who also had at least a 1-point reduction on CGI-TS-S will also be investigated. If there is a strong correlation between subjects ≥6 and <18 years who meet Relapse criteria based on the YGTSS-TTS and have a worsening by at least one category of the CGI-TS-S, Relapse will not be a competing risk, and therefore the time to worsening of the CGI-TS-S for subjects ≥6 and <18 years will be considered a secondary endpoint. Similarly, if there is a strong correlation between all subjects irrespective of age who meet Relapse criteria based on the YGTSS-TTS and have a worsening by at least one category of the CGI-TS-S, Relapse will not be a competing risk, and therefore the time to worsening of the CGI-TS-S for all subjects irrespective of age will be considered a secondary endpoint.

Subgroup analyses will also be conducted on all efficacy endpoints listed above for the following populations:

- Children (≥ 6 and < 12 years of age), Adolescents (≥ 12 and < 18 years of age), and Adults (≥ 18 years of age).
- Subjects per region
- Males and Females
- Ethnicity

Additionally, Time from Randomization to a loss of \geq 50% improvement on the YGTSS-TTS will also be analyzed using the following subgroups:

• Early Responders (at Week 4) and Later Responders (at Week 8)

Rank order of hierarchy of the secondary and exploratory endpoints will be outlined in the statistical analysis plan.

Safety:

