11.3.1. Clinical Global Impression Tourette Syndrome (CGI-TS)^{20,12}

The CGI-TS provides an overall clinician-determined summary assessment that takes into account all available information, including a knowledge of the patient's history, psychosocial circumstances, symptoms, behavior, and the impact of the symptoms on the patient's ability to function.

Administered by an experienced clinician familiar with the disease under study and the likely progression of treatment, the CGI rater can make an expert clinical global judgment about the severity of the illness across various time points within the context of that clinical experience. The clinician makes a judgment about the total health of the subject at each visit: the illness severity, the subject's level of distress and other aspects of impairment, and the impact of the illness on functioning. The CGI is rated without regard to the clinician's belief that any clinical changes are or are not due to medication and without consideration of the etiology of the symptoms.

The CGI consists of two reliable and valid 7-item Likert scales used to assess severity and change in clinical symptoms. The severity scale (CGI-S) ranges from 1 (Normal, not ill) to 7 (extremely ill). The improvement scale (CGI-I) ranges from 1 (very much improved) to 7 (very much worse) with a score of 1 or 2 defining positive resp. nse. Pediatric and adult versions of the CGI-TS-S and CGI-TS-I scales are available and will be administered according to the age of the subject at the time of Informed Consent.

The severity rating is based upon observed and reported symptoms, behavior, and function in the past seven days with the score reflecting the average severity level across the seven days. The efforts of peers, teachers and parents to as ist, accommodate, or support the subject should be considered in overall severity in the case of pediatric subjects.

The improvement rating compares the subject's overall clinical condition to the Baseline visit and the rater should consider the following question: "Compared to tic severity at baseline, how much has the subject changed?" The two CGI-TS scores can occasionally be dissociated such that a clinician may notice changes in the CGI-I relative to baseline despite no recent changes in the overall CGI-S score or vice versa.²¹

The look back period is past 7 days. Administration time is approximately 5 minutes.

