The CGI-TS-S endpoints currently listed as time-to-event exploratory endpoints may be considered as secondary endpoints, if there is a strong correlation between subjects meeting Relapse criteria based on YGTSS-TTS and those who also had at least a 1-point reduction on CGI-TS-S. The strong correlation would suggest Relapse is not a competing risk. Details will be provided in the Statistical Analysis Plan.

The time-to-event estimand for the primary endpoint, which uses the mITT study population, and for the time-to-event secondary and exploratory endpoints related to Relapse will rely on a treatment policy strategy (which also has elements of a composite strategy, in that three intercurrent events, initiation of additional medications and hospitalization for worsening symptoms are incorporated as part of the definition of the primary endpoint). The intercurrent events of loss to follow-up will be assumed unrelated to treatment and treated in estimation as censored observations. Sensitivity analyses for the primary endpoint may assess alternate treatment of such missing data; details will be provided in the Statistical Analysis Plan.

The time-to-event endpoints not related to Relapse will rely on a treatment policy strategy. A cumulative incidence approach will be used to account for the competing risk of study discontinuation due to Relapse. Cause-specific Cox models will be used to obtain the hazard ratio and its 95% CI for time to worsening. In this model, subjects who complete or discontinue from the double-blind randomized withdrawal period before meeting endpoint criteria and for reasons not related to Relapse will be censored at the time of discontinuation. In addition, we will consider graphical and descriptive approaches in correlating the YGTSS with other scores (e.g., CGI-TS-S) in the study subjects across time points.

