### Statistical analysis:

This analysis will be performed irrespective of age. The analysis method will be the same as the secondary efficacy analysis as described in Section 10.2.2.

The correlation in subjects, irrespective of age, between meeting relapse criteria based on YGTSS-TTS and those who had at least a 1-point reduction on CGI-TS-S will be assessed at the visit where relapse occurs. If there is a strong correlation of this endpoint i.e. 100% of subjects who would have met Relapse criteria based on the YGTSS and at least 90% completed CGI-TS-S for subjects with completed YGTSS-TTS, also had at least a 1-point decrease on the CGI-TS-S (i.e. these two types of events occur simultaneously) then it may be considered as a secondary endpoint with agreement from Health Authorities. The strong correlation would suggest Relapse is not a competing risk.

10.2.4. Mean change from Randomization (Week 12) to Week 24 in the YGTSS-TTS for ecopipam compared to placebo.

An exploratory analysis will be performed on the change in YGTSS-TTS from randomization to Week 24.

Statistical analysis:

This document is confidential.

SAP text Version: SAP text 3.0 6-Dec-2023

Controlled Document ID: 3903A.02, Effective Date 31-Aug-2020

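### The SAP rule for promoting time to CGI-TS-S worsening to a secondary endpoint asks for a fall in CGI-TS-S, which on this scale is an improvement

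*SAP*

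**What the plan says.** The scale is described the same way in both documents. SAP 10.2.2: "The severity scale (CGI-TS-S) ranges from 1 (Normal, not ill) to 7 (extremely ill"). Protocol 11.3.1: "The severity scale (CGI-S) ranges from 1 (Normal, not ill) to 7 (extremely ill"). The two endpoints concerned are the times from Randomization (Week 12) to a CGI-TS-S worsening of one category or more, first in subjects aged 6 to under 18 and then in all subjects.

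Both start as exploratory. By default they are analysed with Relapse as a competing risk: cumulative incidence, Gray's test and a cause-specific Cox model. SAP 10.2.2 sets the condition for promotion: all subjects who would have met the YGTSS-based Relapse criterion "also had at least a 1-point decrease on the CGI-TS-S", with a further requirement on CGI-TS-S completeness. If that holds, "it may be considered as a secondary endpoint with agreement from Health Authorities". SAP 10.2.3 repeats the rule for all ages and says that the correlation with "those who had at least a 1-point reduction on CGI-TS-S will be assessed at the visit where relapse occurs".

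The protocol is divided. Section 13.4.1 makes promotion depend on a strong correlation with "those who also had at least a 1-point reduction on CGI-TS-S". In the synopsis, the sentence describing the correlation refers to "at least a 1-point reduction on CGI-TS-S will also be investigated", but the sentence that decides promotion concerns subjects who meet Relapse and "have a worsening by at least one category of the CGI-TS-S, Relapse will not be a competing risk". Protocol 11.3 follows the synopsis in both sentences.

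**The concern.** A promotion rule of this kind should test whether subjects who relapse on the YGTSS also worsen on CGI-TS-S at the same visit. The SAP wording tests whether they improve. Applied literally with Week 12 as the reference, a relapser who worsens counts against promotion. Because the bar is 100%, one such subject is enough to fail it.

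The rule determines whether two endpoints can enter the fixed testing sequence as secondary endpoints, and whether Relapse may be set aside as a competing risk for them. If the direction were corrected only after results were known, the change to endpoint status would look data-driven at the point where Health Authority agreement is sought.

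The rule also does not say which visit the 1-point change is measured from. SAP 8.2 defines both change from baseline and change from randomization.

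**Working it through.** The plan gives no figure for this rule other than the 100% bar, so the check compares wording and counts score pairs.

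**1. Direction of the scale.** With 1 as normal and 7 as extremely ill, a higher score is worse. Protocol 5.2.2 reads it that way: in the open-label extension study, a fall in mean CGI-TS-S from 4.3 to 3.3 at six months is reported in support of efficacy.

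**2. The statements side by side.**

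| Place | Function | Direction stated |
|---|---|---|
| SAP 10.2.2 and 10.2.3, endpoint | defines the event | worsening |
| SAP 10.2.2 and 10.2.3, correlation sentence | describes what is assessed | reduction |
| SAP 10.2.2 and 10.2.3, promotion rule | decides promotion | decrease |
| Protocol 13.4.1 | decides promotion | reduction |
| Protocol synopsis and 11.3, descriptive sentence | describes what is assessed | reduction |
| Protocol synopsis and 11.3, deciding sentences | decide promotion | worsening |

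The reversed word appears seven times: twice in each SAP section and once each in the synopsis, Protocol 11.3 and Protocol 13.4.1. SAP Section 14 records no departures from the protocol, so nothing settles the conflict.

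**3. Overlap of rule and endpoint, measured from Week 12.** Let *a* be the Week 12 score and *b* the Relapse-visit score, each from 1 to 7.

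- Possible pairs: 7 × 7 = 49.
- Rule as written, *a* − *b* ≥ 1: 0+1+2+3+4+5+6 = 21 pairs.
- Endpoint, *b* − *a* ≥ 1: 6+5+4+3+2+1+0 = 21 pairs.
- No change: 7 pairs.
- Pairs meeting both: 0.

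For example, from a Week 12 score of 4 the endpoint is met by 5, 6 or 7 and the rule by 1, 2 or 3. If *n* subjects relapse on the YGTSS and all worsen on CGI-TS-S, the rule as written counts 0 of *n* and the intended rule *n* of *n*.

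**4. Dependence on the reference visit.** Take scores of 5 at Baseline, 3 at Week 12 and 4 at Relapse. From Baseline, 4 − 5 = −1, a 1-point decrease that passes the rule as written. From Week 12, 4 − 3 = +1, a worsening that fails it. The result for this subject depends on a choice the SAP does not state.

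**5. How much a corrected rule would change in practice.** Suppose all 49 planned Relapse events (SAP 4.3) are YGTSS-based and each independently shows CGI-TS-S worsening with probability *p*. The documents give no value for *p*, so a range is assumed. The chance that all 49 agree is *p*^49:

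- *p* = 0.90: 0.6%
- *p* = 0.95: 8.1%
- *p* = 0.99: 61%

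**The case against.** The strongest reply is that the intent is plain. The same SAP sentence goes on to explain that the two kinds of event happen at the same time, and the rule refers back to the section's own endpoint, which is a worsening. A programmer would have to disregard the title, the endpoint definition and that explanation to apply the rule backwards. Week 12 is likewise the natural reference, since the endpoint runs from Randomization. The SAP also did not depart from a clear protocol: it agrees with Protocol 13.4.1 and conflicts with the synopsis and Protocol 11.3. Finally, the stakes are small. Promotion is optional and needs Health Authority agreement, a 100% bar may well fail even in the right direction, and a literal reading errs conservatively by leaving two endpoints exploratory.

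Much of this stands. It is very probably a wording slip, the protocol is itself inconsistent, and no type I error is inflated. The pair count shows only that rule and endpoint exclude each other; it is not a probability for this trial. But evident intent does not make the operative words right. This is a decision rule that will be applied to data, and it is reversed wherever the SAP states it. A corrected rule that is hard to meet can still be met; the rule as written, taken from Week 12, cannot be met by any relapser who worsens.

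**Conclusion.** The concern holds. As written, the promotion rule in SAP 10.2.2 and 10.2.3 requires improvement on CGI-TS-S. It contradicts the endpoint it serves and the deciding sentences in the protocol synopsis and Protocol 11.3, while sharing its error with Protocol 13.4.1. With Week 12 as the reference, full agreement between Relapse and CGI-TS-S worsening scores 0 of *n* instead of *n* of *n*. The conclusion rests on the documented scale direction and on Week 12 as the reference; with Baseline as the reference the outcome would vary by subject.

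The consequence is confined to whether two endpoints, placed last in the testing order, can become secondary or stay exploratory under the competing-risk analysis. The primary endpoint, the named secondary endpoint, alpha, power and the planned 49 events do not change. It should be corrected before unblinding.

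**What to change.** In SAP 10.2.2 and 10.2.3, replace the reduction and decrease wording, in both the correlation sentence and the promotion rule, with *an increase (worsening) of at least 1 point from Randomization (Week 12) at the Relapse visit*. This corrects the direction and names the reference. Record in SAP Section 14 that it corrects the wording of Protocol 13.4.1. At the next protocol amendment, align Protocol 13.4.1 and the descriptive sentences in the synopsis and Protocol 11.3.

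The cost is a wording edit in two SAP sections and one note, with no new data or analysis. The protocol edits can wait for an amendment that is needed anyway, because amendments go through IRB/IEC approval (Protocol 16.1).

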### Statistical analysis:

This analysis will be performed irrespective of age. The analysis method will be the same as the secondary efficacy analysis as described in Section 10.2.2.

The correlation in subjects, irrespective of age, between meeting relapse criteria based on YGTSS-TTS and those who had at least a 1-point reduction on CGI-TS-S will be assessed at the visit where relapse occurs. If there is a strong correlation of this endpoint i.e. 100% of subjects who would have met Relapse criteria based on the YGTSS and at least 90% completed CGI-TS-S for subjects with completed YGTSS-TTS, also had at least a 1-point decrease on the CGI-TS-S (i.e. these two types of events occur simultaneously) then it may be considered as a secondary endpoint with agreement from Health Authorities. The strong correlation would suggest Relapse is not a competing risk.

10.2.4. Mean change from Randomization (Week 12) to Week 24 in the YGTSS-TTS for ecopipam compared to placebo.

An exploratory analysis will be performed on the change in YGTSS-TTS from randomization to Week 24.

Statistical analysis:

This document is confidential.

SAP text Version: SAP text 3.0 6-Dec-2023

Controlled Document ID: 3903A.02, Effective Date 31-Aug-2020

The mean change from Randomization (Week 12) to Week 24 (Weeks 13,14,15,16,18,20, 22 and 24) in YGTSS-TTS will be summarized. This endpoint will be analyzed with a Mixed Model for Repeated Measures (MMRM) model using the SAS MIXED procedure with REPEATED statement. The model with an unstructured covariance matrix will include fixed effects for treatment, visit, interaction between treatment and visit, region, age group (0 = children 6-11, 1 = adolescents 12-17, 2=adults >=18) and covariate for week 12 YGTSS-TTS. Visit will include weeks 13,14,15,16,18, 20, 22 and 24. By visit comparisons will be provided. In the event the model does not converge using the standard unstructured covariance matrix, the Fisher scoring algorithm to obtain initial values of covariance parameters will be tried. If this method fails to converge, the FA0(T) structure will be tried. Following failure of this method, the successive univariate method proposed by Lu and Mehrotra (2010) will be tried. In the event all the previous methods fail to converge, the autoregressive and Toeplitz structures will be tried, and a sandwich estimator for the treatment effect estimate will be implemented. The final covariance structure will be documented in the table. All observed endpoint data will be used in this analysis, without imputation.

Summary statistics will be presented along with a full data listing by treatment group.

10.2.5. Mean change from Randomization (Week 12) to Week 24 in the CGI-TS-S for ecopipam compared to placebo.

An exploratory analysis will be performed on the change in CGI-TS-S from randomization to Week 24.

# Statistical analysis:

The mean change from Randomization (Week 12) to Week 24 (Weeks 13,14,15,16,18,20, 22 and 24) in CGI-TS-S will be summarized. This endpoint will be analyzed with a Mixed Model for Repeated Measures (MMRM) model using the SAS MIXED procedure with REPEATED statement. The model with an unstructured covariance matrix will include fixed effects for treatment, visit, interaction between treatment and visit, region, age group (0 = children 6-11, 1 = adolescents 12-17, 2=adults >=18) and covariate for week 12 CGI-TS-S. Visit will include weeks 13,14,15,16,18,20, 22 and 24. By visit comparisons will be provided. In the event the model does not converge using the unstructured covariance matrix, the methods described in Section 10.2.4 will be tried. The final covariance structure will be documented in the table. All observed endpoint data will be used in this analysis, without imputation. Summary statistics will be presented along with a full data listing by treatment group.

10.2.6. Mean change from Randomization (Week 12) to Week 24 in the YGTSS-Global Severity (GS) Score for ecopipam compared to placebo.

An exploratory analysis will be performed on the change in YGTSS-Global score (GS) from randomization to Week 24.

